## **6.6. Assessments for Premature Discontinuation from Study**

If a subject prematurely discontinues study treatment (see Section 3.5.1, Discontinuation of Study Treatment), every attempt should be made to keep the subject in the study and continue to perform the required study-related follow-up and procedures (see Sections 6.8). If this is not possible or acceptable to the subject or investigator, the subject may be withdrawn from the study and no further study-related follow-up and procedures will be performed.

## **6.7. End of Treatment**

Subjects will be removed from study treatment when any of the criteria listed in Section 3.5.1 apply. The following procedures will be conducted when a subject discontinues study treatment and prior to initiating a new therapy.

- Review concomitant medications
- Review any AEs
- Performance status
- Physical exam
- Vital signs; including blood pressure, respiratory rate, pulse, temperature, oxygen saturation level
- Weight
- Obtain blood samples for:
  - Chemistry
  - Hematology (with differential)
  - Coagulation
- Urine Pregnancy Test (for females of childbearing potential)
- Subjects with AML will undergo a bone marrow aspirate and biopsy for disease assessment (~8mL) (if not performed within the last 2 weeks). Subjects with cytogenetic and molecular mutations at screening must have cytogenetic and molecular mutation testing repeated.
- Subjects with hematologic malignancies other than AML will undergo the appropriate clinical, radiographic, and laboratory procedures per the standard of care or institutional practice for disease assessment (if not performed within the last 2 weeks)

## **6.8. Follow-up**

### **6.8.1. Remission/Relapse**

Subjects with AML who achieve remission or relapse should undergo a bone marrow aspirate and biopsy for disease assessment (~8mL) and have a blood sample obtained for hematology. Subjects with cytogenetic and molecular mutations at screening must have cytogenetic and molecular mutation testing repeated.

Subjects with hematologic malignancies other than AML will undergo the appropriate clinical, radiographic, and laboratory procedures per the standard of care or institutional practice for disease assessment.

### **6.8.2. 30-day Follow-up**

Subjects will be contacted by telephone 30 days ( $\pm$  7 days) after the last dose of ENTO to assess AEs and review concomitant medications. The 30-day follow-up visit may be substituted by a scheduled study visit if it occurs within the same window.

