#### Adverse Events

Following initiation of study medication, collect all AEs, regardless of cause or relationship, until 30 days after last administration of study IMP must be reported to the eCRF database as instructed.

All AEs should be followed up until resolution or until the AE is stable, if possible. Gilead Sciences may request that certain AEs be followed beyond the protocol defined follow up period.

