### **8.6.2. Adverse Events**

All AEs will be listed. The AE summarization will focus on treatment-emergent AEs. Treatment-emergent AEs are defined as AEs that onset in the period from the first dose of study treatment to 30 days after the permanent discontinuation of study treatment or that lead to permanent study treatment discontinuation.

AEs that occur before the first dose of study treatment or >30 days after study treatment discontinuation will be included in data listings.

AEs will be classified using Medical Dictionary for Regulatory Activities (MedDRA) with descriptions by System Organ Class, High-Level Group Term, High Level Term, Preferred Term, and Lower-Level Term. The severity of AEs will be graded by the investigator according to the CTCAE, Version 4.03 (<http://www.hrc.govt.nz/sites/default/files/CTCAE%20manual%20-%20DMCC.pdf>), whenever possible. If a CTCAE criterion does not exist for a specific type of AE, the grade corresponding to the appropriate adjective will be used by the investigator to describe the maximum intensity of the AE: Grade 1 (mild), Grade 2 (moderate), Grade 3 (severe), Grade 4 (life threatening), or Grade 5 (fatal). The relationship of the AE to study treatment will be categorized as related or unrelated.

Treatment-emergent AEs will be summarized by presenting the number and percentage of subjects with treatment-emergent AEs by severity grade. Subjects who report multiple treatment-emergent AEs under the same Preferred Term (or System Organ Class) are counted only once under the worst severity grade. The summary will be presented in decreasing frequency of System Organ Class and Preferred Term of the 'Total' column. Within the same frequency, the AEs are ordered in the alphabetical order of System Organ Class and Preferred Term. Separate listings and summaries will be provided for the following types of treatment-emergent AEs:

- Study treatment related AEs
- AEs with severity  $\geq$  Grade 3
- AEs leading to study treatment interruption and/or dose modification
- AEs leading to study treatment discontinuation
- Study treatment related SAEs
- DLT
- DLT rates and their 90% CI

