#### **7.1.5. Treatment-Emergent Adverse Events**

##### **7.1.5.1. Definition of Treatment-Emergent Adverse Events**

Treatment-emergent adverse events (TEAEs) are defined as 1 or both of the following:

- Any AEs with an onset date on or after the study drug start date and no later than 30 days after permanent discontinuation of study drug
- Any AEs leading to premature discontinuation of study drug

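### The last planned AE contact may fall as early as day 23 after the last dose, up to 7 days before AE collection and the treatment-emergent window end, so late non-serious TEAEs could be missed

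*Protocol*

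**What the plan says.** **The contact.** Protocol 6.8.2 provides one telephone contact: "Subjects will be contacted by telephone 30 days", with a tolerance of 7 days in each direction, counted from the last ENTO dose. Its purpose is to review AEs and concomitant medications. It "may be substituted by a scheduled study visit if it occurs within the same window". The procedures tables in Protocol Appendices 2 and 3, and the Group A table repeated in SAP Appendix 1, give the same tolerance.

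**The period it serves.** Protocol 7.3 tells sites to "collect all AEs, regardless of cause or relationship, until 30 days after last administration of study IMP". Protocol 8.6.2 defines treatment-emergent AEs as those with onset "from the first dose of study treatment to 30 days after the permanent discontinuation of study treatment" (or that lead to permanent discontinuation). SAP 7.1.5.1 sets the same limit: "no later than 30 days after permanent discontinuation of study drug". Protocol 6.2.9 is looser and describes AE assessment to approximately day 30.

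**What comes afterwards.** Long-term follow-up (Protocol 6.8.3) is six-monthly, with a tolerance of 4 weeks, and records leukemia treatments, other malignancies and survival. The AE row of the procedures tables has no mark there, nor at the remission/relapse visit in Appendix 2 or the relapse visit in Appendix 3.

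**The partial safeguard.** The SAE part of Protocol 7.3 requires SAEs and deaths arising after the follow-up visit, but within 30 days of the last dose, to be reported whatever their cause. The AE part has no matching sentence for non-serious events that start after the contact.

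**The concern.** The tolerance is symmetric, but its two halves do different things. A late call still looks back over the whole 30 days. An early call cuts the observed period short, and nothing planned afterwards asks about the days that remain. The duty to collect AEs to day 30 continues, but after an early call it relies on the subject volunteering the event or on the site making an unscheduled enquiry.

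What is at stake is the completeness of the AE summaries. AEs other than DLTs are a secondary safety endpoint (Protocol 3.1 and 8.1.3), and the TEAE tables in SAP 7.1.6 count events by this window. If contact days differ between subjects, so does the period actively asked about, although every table treats it as 30 days.

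**Working it through.** The plan states no figure for this gap, so there is none to reproduce. The check is date arithmetic.

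**Inputs**
- Nominal contact day: 30 after the last ENTO dose (Protocol 6.8.2)
- Tolerance: 7 days either way (Protocol 6.8.2, Appendices 2 and 3; SAP Appendix 1)
- End of AE collection and of the treatment-emergent window: day 30 (Protocol 7.3 and 8.6.2; SAP 7.1.5.1)
- Subjects enrolled: 9 (SAP 3)

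**Step 1: permitted contact days.** 30 − 7 = 23 to 30 + 7 = 37, which is 15 days.

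**Step 2: days without a planned AE contact.** For a contact on day d, gap(d) = max(0, 30 − d).

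| Contact day | 23 | 24 | 25 | 26 | 27 | 28 | 29 | 30 to 37 |
|---|---|---|---|---|---|---|---|---|
| Gap (days) | 7 | 6 | 5 | 4 | 3 | 2 | 1 | 0 |

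**Step 3: size.**
- Worst case: days 24 to 30, so 7/30 = 23.3% of the post-treatment period.
- Permitted days that leave some gap: 7 of 15. The other 8 leave none.
- If contacts were spread evenly over the window (an assumption, since the documents do not give actual call dates): (7 + 6 + 5 + 4 + 3 + 2 + 1)/15 = 28/15 = 1.9 days on average, about 6% of 30.
- Upper bound for the study, with all 9 subjects contacted on day 23: 9 × 7 = 63 of 9 × 30 = 270 subject-days.

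**Step 4: can a later contact recover the gap?** The earliest long-term contact is 6 months less 4 weeks, about 182.6 − 28 = 155 days after EOT. It would show a death through the survival enquiry, but AE review is not part of it.

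**Step 5: effect of a +7-only tolerance.** Permitted days become 30 to 37, and gap(d) = 0 for each of them.

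**The case against.** The strongest reply is that the protocol foresees an early contact. Protocol 7.3 keeps SAEs and deaths reportable after the follow-up visit and up to day 30, and its general instruction to collect all AEs to day 30 is not lifted by an early call. Protocol 6.2.9 speaks of approximately 30 days, which suits a nominal day-30 contact with an ordinary tolerance. On this view the passages do not contradict each other. That much stands, and it narrows the point to non-serious AEs that start after an early call and that the site does not otherwise hear of. It does not remove the point: neither passage schedules a contact to find such events, and the approximate wording in 6.2.9 does not move the day-30 limit in 7.3, 8.6.2 or the SAP.

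A second reply is that little depends on the call. For Group A, DLTs are assessed over Cycle 1 Days 1 to 28 (Protocol 3.2.1). SAP 1.3 states that no safety hypothesis is tested, and the summaries describe 9 subjects at one dose level (SAP 3 and 3.2). This stands too. A reader might infer from the gap that the primary safety endpoint is compromised; the documents do not support that.

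A reader might also infer that TEAEs are in fact under-counted. That needs three things together: a contact before day 30, a new event between that contact and day 30, and no other route by which the site learns of it. The documents do not show that any call was early or any event missed. The supportable statement is that events could be missed.

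**Conclusion.** The point holds as a minor one. A compliant contact can leave up to 7 of the 30 post-treatment days (23%) without a planned AE enquiry. That is the worst case, not the expected loss: a contact on days 30 to 37 leaves no gap, and an even spread of contact days would average 1.9 days. Nor are the days in the gap wholly unobserved, because the reporting duties in 7.3 continue. The exposure is late non-serious TEAEs in the secondary, descriptive summaries.

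The conclusion assumes that permanent discontinuation is dated at the last ENTO dose. The call counts from the last dose, and the treatment-emergent window counts from permanent discontinuation. If discontinuation were dated later, for example after a dose hold, the gap could exceed 7 days, although a correspondingly later EOT visit, which reviews AEs, might cover part of it.

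**What to change.** In Protocol 6.8.2, set the contact at 30 days with a tolerance of +7 days only. Allow substitution only by a scheduled visit on or after day 30 within that window. Make the same change to the follow-up column in Protocol Appendices 2 and 3 and in the SAP Appendix 1 copy.

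This uses the same single call and keeps a week of flexibility. The cost is the loss of the early week for scheduling and a minor protocol amendment, which needs IEC approval (Protocol 9.2.1). The Appendix 3 change is for consistency only, since Group B did not open (SAP 1).

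If subjects have already passed this contact, adding the date of last AE contact to the by-subject listing in SAP 4.1 would show how many were actually followed to day 30. That listing gives the last dose date but not the contact date.

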### **6.8.3. Long Term Follow-up**

Long term follow-up (LTFU) for OS begins after EOT or the last study visit if EOT does not occur. Subjects will be contacted by telephone or during a routine clinic visit every 6 months ( $\pm$  4 weeks) to gather leukemia treatments, other malignancies, and survival for up to 3 years after EOT or the last study visit. Every attempt should be made to keep the subject in LTFU for OS.

## 7. ADVERSE EVENTS AND TOXICITY MANAGEMENT

### 7.1. Definitions of Adverse Events, Adverse Reactions, and Serious Adverse Events

#### 7.1.1. Adverse Events

An adverse event (AE) is any untoward medical occurrence in a clinical study subject administered a medicinal product, which does not necessarily have a causal relationship with the treatment. An AE can therefore be any unfavorable and/or unintended sign, symptom, or disease temporally associated with the use of a medicinal product, whether or not considered related to the medicinal product. AEs may also include pre- or post-treatment complications that occur as a result of protocol specified procedures, lack of efficacy, overdose, drug abuse/misuse reports, or occupational exposure. Preexisting events that increase in severity or change in nature during or as a consequence of participation in the clinical study will also be considered AEs.

An AE does not include the following:

- Medical or surgical procedures such as surgery, endoscopy, tooth extraction, and transfusion. The condition that led to the procedure may be an AE and must be reported.
- Pre-existing diseases, conditions, or laboratory abnormalities present or detected before the screening visit that do not worsen
- Situations where an untoward medical occurrence has not occurred (eg, hospitalization for elective surgery, social and/or convenience admissions)
- Overdose without clinical sequelae
- Any medical condition or clinically significant laboratory abnormality with an onset date before the consent form is signed and not related to a protocol-associated procedure is not an AE. It is considered to be pre-existing and should be documented on the medical history CRF.

#### 7.1.2. Serious Adverse Events

A **serious adverse event** (SAE) is defined as an event that, at any dose, results in the following:

- Death
- Life-threatening (Note: The term “life-threatening” in the definition of “serious” refers to an event in which the subject was at risk of death at the time of the event; it does not refer to an event that hypothetically might have caused death if it were more severe.)
- In-patient hospitalization or prolongation of existing hospitalization

- Persistent or significant disability/incapacity
- A congenital anomaly/birth defect
- A medically important event or reaction: such events may not be immediately life-threatening or result in death or hospitalization but may jeopardize the subject or may require intervention to prevent one of the other outcomes constituting SAEs. Medical and scientific judgment must be exercised to determine whether such an event is a reportable under expedited reporting rules. Examples of medically important events include intensive treatment in an emergency room or at home for allergic bronchospasm; blood dyscrasias or convulsions that do not result in hospitalization; and development of drug dependency or drug abuse. For the avoidance of doubt, infections resulting from contaminated medicinal product will be considered a medically important event and subject to expedited reporting requirements.

#### 7.1.2.1. Protocol-Specific Serious Adverse Event Instructions

Disease Progression and Death Related to Disease Progression: Given the endpoints of the study, in order to maintain the integrity of the study, the following events that are assessed as unrelated to study drugs will not be considered SAEs:

- Progression of malignancy being studied
- Death due to malignancy being studied

Disease progression and death from disease progression should be reported as SAEs by the investigator only if it is assessed that the study drugs caused or contributed to the disease progression (ie, by a means other than lack of effect). Unrelated disease progression should be captured on the eCRF.

These events will be reported, as appropriate, in the final clinical study report and in any relevant aggregate safety reports.

Protocol-specific SAE reporting exemptions: Subjects with AML may be profoundly anemic and thrombocytopenic secondary to bone marrow involvement by their AML or from the myelosuppressive effects of chemotherapy. These subjects will thus require transfusional support with red cells and platelets per institutional guidelines and therefore may require hospitalization for transfusions.

#### 7.1.3. **Clinical Laboratory Abnormalities and Other Abnormal Assessments as Adverse Events or Serious Adverse Events**

Laboratory abnormalities without clinical significance are not recorded as AEs or SAEs. However, laboratory abnormalities (eg, clinical chemistry, hematology, and urinalysis) that require medical or surgical intervention or lead to IMP interruption, modification, or discontinuation must be recorded as an AE, as well as an SAE, if applicable. In addition,

laboratory or other abnormal assessments (eg, electrocardiogram, x-rays, vital signs) that are associated with signs and/or symptoms must be recorded as an AE or SAE if they meet the definition of an AE or SAE as described in Section 7.1. If the laboratory abnormality is part of a syndrome, record the syndrome or diagnosis (eg, anemia), not the laboratory result (ie, decreased hemoglobin).

For specific information on handling of clinical laboratory abnormalities in this study, please refer to Section 7.1.3.

## **7.2. Assessment of Adverse Events and Serious Adverse Events**

The investigator or qualified subinvestigator is responsible for assessing AEs and SAEs for causality and severity, and for final review and confirmation of accuracy of event information and assessments.

### **7.2.1. Assessment of Causality for Study Drugs and Procedures**

The investigator or qualified subinvestigator is responsible for assessing the relationship to IMP therapy using clinical judgment and the following considerations:

- **No:** Evidence exists that the AE has an etiology other than the IMP. For SAEs, an alternative causality must be provided (eg, pre-existing condition, underlying disease, intercurrent illness, or concomitant medication).
- **Yes:** There is reasonable possibility that the event may have been caused by the investigational medicinal product.

It should be emphasized that ineffective treatment should not be considered as causally related in the context of AE reporting.

The relationship to study procedures (eg, invasive procedures such as venipuncture or biopsy) should be assessed using the following considerations:

- **No:** Evidence exists that the AE has an etiology other than the study procedure.
- **Yes:** The AE occurred as a result of protocol procedures (eg, venipuncture)

### **7.2.2. Assessment of Severity**

The severity of AEs will be graded using the CTCAE, Version 4.03 (see Section 8.6.2). For each episode, increasing grade changes should be reported.

If a CTCAE criterion does not exist, the investigator should use the grade or adjectives: Grade 1 (mild), Grade 2 (moderate), Grade 3 (severe), Grade 4 (life-threatening), or Grade 5 (fatal) to describe the maximum intensity of the AE. For purposes of consistency with the CTCAE, these intensity grades are defined below.

## Grading of Adverse Event Severity

Grade	Adjective Description
Grade 1	Mild Sign or symptom is present, but it is easily tolerated, is not expected to have a clinically significant effect on the subject's overall health and well-being, does not interfere with the subject's usual function, and is not likely to require medical attention.
Grade 2	Moderate Sign or symptom causes interference with usual activity or affect clinical status, and may require medical intervention.
Grade 3	Severe Sign or symptom is incapacitating or significantly affects clinical status and likely requires medical intervention and/or close follow-up.
Grade 4	Life-threatening Sign or symptom results in a potential threat to life.
Grade 5	Fatal Sign or symptom results in death.

The distinction between the seriousness and the severity of an AE should be noted. Severe is a measure of intensity; thus, a severe reaction is not necessarily a serious reaction.

### 7.3. Investigator Requirements and Instructions for Reporting Adverse Events and Serious Adverse Events to Gilead

Requirements for collection prior to study drug initiation:

After informed consent, but prior to initiation of study medication, the following types of events should be reported on the case report form (eCRF): all SAEs and AEs related to protocol-mandated procedures.

#### Adverse Events

Following initiation of study medication, collect all AEs, regardless of cause or relationship, until 30 days after last administration of study IMP must be reported to the eCRF database as instructed.

All AEs should be followed up until resolution or until the AE is stable, if possible. Gilead Sciences may request that certain AEs be followed beyond the protocol defined follow up period.

#### Serious Adverse Events

All SAEs, regardless of cause or relationship, that occurs after the subject first consents to participate in the study (ie, signing the informed consent) and throughout the duration of the study, including the protocol-required post treatment follow-up period, must be reported to the eCRF database and Gilead Drug Safety and Public Health (DSPH) as instructed. This also includes any SAEs resulting from protocol-associated procedures performed after informed consent is signed.

Any SAEs and deaths that occur after the post treatment follow-up visit but within 30 days of the last dose of study IMP, regardless of causality, should also be reported.

Investigators are not obligated to actively seek SAEs after the protocol defined follow up period however, if the investigator learns of any SAEs that occur after study participation has concluded and the event is deemed relevant to the use of IMP, he/she should promptly document and report the event to Gilead DSPH.

- All AEs and SAEs will be recorded in the eCRF database within the timelines outlined in the eCRF completion guideline.

#### **Electronic Serious Adverse Event (eSAE) Reporting Process**

- Site personnel record all SAE data in the eCRF database and from there transmit the SAE information to Gilead DSPH and Gilead Japan DSPH within 24 hours of the investigator's knowledge of the event. Detailed instructions can be found in the eCRF completion guidelines.
- If for any reason it is not possible to record the SAE information electronically (ie, the eCRF database is not functioning) record the SAE on the paper SAE reporting form and submit within 24 hours to Gilead DSPH. Fax: PPD or email: PPD
- As soon as it is possible to do so, any SAE reported via paper must be transcribed into the eCRF Database according to instructions in the eCRF completion guidelines.
- If an SAE has been reported via a paper form because the eCRF database has been locked, no further action is necessary.
- For fatal or life-threatening events, copies of hospital case reports, autopsy reports, and other documents are also to be submitted by e-mail or fax when requested and applicable. Transmission of such documents should occur without personal subject identification, maintaining the traceability of a document to the subject identifiers.
- Additional information may be requested to ensure the timely completion of accurate safety reports.
- Any medications necessary for treatment of the SAE must be recorded onto the concomitant medication section of the subject's eCRF and the event description section of the SAE form.

